#### *VARC-3 Minor Vascular Complications*

One of the following:

- Vascular (arterial or venous) injury (perforation, rupture, dissection, stenosis, ischaemia, arterial or venous thrombosis including pulmonary embolism, arteriovenous fistula, pseudoaneurysm, haematoma, retroperitoneal haematoma, infection) not resulting in death, VARC type  $\geq 2$  bleeding, limb or visceral ischaemia, or irreversible neurologic impairment
- Distal embolization treated with embolectomy and/or thrombectomy, not resulting in death, amputation, limb or visceral ischaemia, or irreversible end-organ damage
- Any unplanned endovascular or surgical intervention, ultrasound guided compression, or thrombin injection, not resulting in death, VARC type  $\geq 2$  bleeding, limb or visceral ischaemia, or irreversible neurologic impairment
- Closure device failure‡ not resulting in death, VARC type  $\geq 2$  bleeding, limb or visceral ischaemia, or irreversible neurologic impairment

A failure to achieve hemostasis at the access site, resulting in alt. treatment (other than manual compression or adjunctive endovascular ballooning)

Essential Medical

Prospective Multicenter MANTA™ Vascular Closure Device
Ultrasound Guided Closure Study (MANTA ULTRA Closure)
Protocol No. ST-3370

Statistical Analysis Plan

ST-3387, Version B

February 02, 2022

Prepared by

[name], Technomics Research LLC

Table of Contents

1	Purpose	3
2	Background	3
2.1	Table 1. Data collection schedule	4
3	Clinical Events Committee	5
4	Data & Safety Monitoring Committee	5
5	Sample Size Requirements.....	5
6	Statistical Analyses and Study Objectives.....	7
6.1	Cohort Definitions.....	7
6.2	Timing of Reports.....	7
6.3	Primary Safety Endpoint: LBAR Major complications	7
6.4	Secondary Endpoints	9
6.4.1	Secondary Endpoint 1: Time to Hemostasis (Effectiveness).....	9
6.4.2	Secondary Endpoint 2: Technical Success (Effectiveness)	9
6.4.3	Secondary Endpoint 3: Ambulation Success (Effectiveness)	9
6.4.4	Secondary Endpoint 4: Time to Ambulation (Effectiveness)	9
6.4.5	Secondary Endpoint 5: Treatment Success (Effectiveness)	10
6.4.6	Secondary Endpoint 6: Procedure Time (Effectiveness).....	10
6.5	Secondary Endpoint 7: LBAR Minor Complications (Safety).....	10
6.6	Additional Analyses.....	11
6.7	Adverse Events and Device Deficiencies.....	11
7	Poolability of Data.....	11
8	Data Conventions and Missing Data	12
9	Appendices:.....	12
9.1	Appendix 1: Definitions of Relatedness of Adverse Events	12
9.2	Appendix 2: Definitions from the Protocol	14
10	References	18

1 Purpose

This Statistical Analysis Plan (SAP) is intended to provide additional details for planned summaries of the data in support of generating a final report for the clinical study, "Prospective Multicenter MANTA™ Vascular Closure Device Ultrasound Guided Closure Study," protocol ID ST-3370, Version A.

All analyses will be performed using validated statistical software such as SAS version 9.4 or other well-known statistical packages.

Note that a separate tables/figures/listings (TFL) template will be prepared separately in support of this SAP to help clarify expected summaries for the Sponsor.

2 Background

The MANTA ULTRA trial is a prospective single arm trial designed to evaluate the safety of ultrasound (U/S) guided deployment of MANTA Vascular Closure Device (VCD). The MANTA device has been previously approved for use in the U.S., and this trial is focused on the addition of using ultrasound to establish the safety of U/S guided closure with MANTA VCD.

All subjects enrolled are expected to undergo Transcatheter aortic valve replacement (TAVR) procedures and a report will be prepared for submission to FDA for approval once the first 75 consecutively enrolled subjects, with a maximum of 15 subjects per site, have reached 30 days.

A total of 150 subjects, with a maximum of 30 subjects per site, undergoing elective TAVR procedures utilizing a femoral arterial access site with a MANTA VCD closure device will be evaluated. Additionally, up to 2 roll-in subjects per operator will be enrolled to allow investigators to learn how to use MANTA VCD ultrasound guided closure technique

The data collection schedule is provided in Table 1 below.

2.1 Table 1. Data collection schedule

Assessment	Screening Visit	TAVR Procedure	Closure Procedure			Post-procedure	Discharge	Follow-up (FUP)	
			Pre	During	Post			30 Day (±7 Days)	12 Month (±30 Days)
Subject Eligibility / Informed Consent / Applicable PHI Authorization form*	X								
Medical History	X								
Medications ¹	X	X	X	X	X	X	X	X	X
Laboratory Tests	X ²								
Pregnancy Test	X ⁹								
CT Angiographic Scan	X ³								
Ultrasound ⁴ (access and assessment)		X		X					
ACT / SBP			X ⁵						
Adjunctive Devices				X	X				
Target Femoral angiography					X ⁶				
Target Femoral access site assessment					X	X	X	X	X ⁷
Time to Hemostasis					X ⁸				
Delayed Ambulation/Discharge						X	X		
Adverse Events			X	X	X	X	X	X	X ⁷
Subsequent Secondary Intervention					X	X	X	X	X

*Or other form required by applicable U.S. or Canadian laws governing the use and disclosure of individually identifiable protected health information (PHI)

1. The following medications will be recorded on the eCRF for each subject: cardiovascular medications (e.g., anti-hypertensives, anti-arrhythmic, etc.), anti-coagulants, anti-thrombotic and anti-platelets. Any changes to these medications should be documented throughout the course of the 12 month follow up.
2. Considered standard of care and are to be done according to the site's standard of care practice for pre-procedure labs for the TAVR procedure (hemoglobin, creatinine, and platelet count, International Normalized Ratio (INR))
3. Screening Visit CT Scan to assess both limbs for presence/absence/severity of calcium, atherosclerotic disease, tortuosity, and acceptable flow rates
4. Ultrasound for access SOC; Ultrasound data collection during closure
5. Prior to all closure methods, record ACT and systolic BP (per MANTA VCD warnings SBP<180mmHg; recommend ACT<250 seconds prior to closure)
6. Post-closure, perform target (ipsilateral) femoral angiography from contralateral access site to ensure patency into the ipsilateral common femoral artery
7. At 12m follow-up, target femoral access site assessment will be questions completed via phone; adverse events will only pertain to target access site
8. The elapsed time between MANTA deployment (withdrawal of sheath from artery) and first observed and confirmed arterial hemostasis (no or minimal subcutaneous oozing and the absence of expanding or developing hematoma).
9. Female subjects of child bearing potential only. Test to be conducted within 7 days of TAVR procedure or according to standard of care for TAVR procedures requiring contrast and angiography. Urine pregnancy test is acceptable.
10. Any additional surgical or percutaneous interventions post the index large bore procedure that occurred on the MANTA (ipsilateral) leg, such as percutaneous coronary intervention (PCI), through the 12 month phone follow-up

3 Clinical Events Committee

An independent Clinical Events Committee (CEC) will be established for this study. The CEC will consist of three interventional cardiologist physicians. CEC members will be physicians chosen based on their clinical expertise and have no association with this study for which they will adjudicate events. Prior to the start of subject enrollment, the CEC will approve a charter containing criteria for event evaluation.

The CEC will be responsible for adjudicating the following events and determining their device and procedure relatedness:

- All Adverse Events that are categorized by the investigator on the eCRF as “associated with the target artery and/or the ipsilateral leg (not the contralateral side)”;
- All Adverse Events marked on the eCRF that are categorized by the investigator as having a possible, probable or causal relationship with the MANTA device.

The CEC will classify each AE as to whether it is a Large Bore Access-site Related VARC-2 Major Vascular complication (LBAR Major) or Large Bore Access-site Related VARC-2 Minor Vascular complication (LBAR Minor) complication or neither. Analysis of the primary and secondary safety endpoints will be based on CEC adjudicated data.

In some cases, grouping of inter-related adverse events into a primary adverse event may be appropriate due to all events being symptoms of the same incident. The CEC will select the primary event among the inter-related site reported events.

4 Data & Safety Monitoring Committee

A Data & Safety Monitoring Committee (DSMC) will be established for this study. The DSMC will be independent from the Sponsor and the study investigators. It will consist of at least three (3) members: two interventional cardiologist physicians that will also act on the CEC and an independent statistician; the two physicians must have extensive experience with large-bore cardiovascular interventions, preferably experience using the MANTA VCD. The DSMC will be established and operate according to a charter defined prior to the initiation of the trial. The DSMC will review cumulative adverse event data and will recommend study termination if safety concerns warrant such action. If the DSMC believes it is possible to predict adverse events, guideline criteria for recommending study termination will be established before enrollment in the study begins. The DSMC will meet by phone or face-to-face, at least two times during the study in order to assure close and timely monitoring of adverse events and outcomes.

5 Sample Size Requirements

The performance goal and the postulated event rate in the prospective study population are based upon clinical judgement supported by outcomes from comparable published studies in Table 2 below; in particular rows pertaining to studies of similar size to the proposed 75 patients are shown in bold. Results for all studies shown used VARC-2 definitions.

Table 2. Safety Performance of MANTA from published literature

Reference	N MANTA VCD subjects	VARC-2 Major Complication			95% Confidence Interval*
		Essential Medical Sponsored	Independent MANTA VCD Studies	Overall	
Van Mieghem 2017 (CE Mark)¹	50	2.0%		2.0%	0.0%, 10.6%
Wood 2019 (IDE Study) ²	263	4.2%		4.2%	2.1%, 7.4%
Van Mieghem 2020 (MARVEL) ³	500	4.0%		4.0%	2.5%, 6.1%
Biancari 2018⁴	107		9.3%	9.3%	4.6%, 16.5%
DePalma 2018⁵	89		1.1%	1.1%	0.0%, 6.1%
Gheorghe 2019 ⁶	169		0.6%	0.6%	0.0%, 3.3%
Hoffman 2018⁷	75		10.7%	10.7%	4.7%, 19.9%
Moccetti 2019⁸	100		7.0%	7.0%	2.8%, 13.9%
Moriyama 2019⁹	111		7.0%	7.0%	3.2%, 13.7%
Van Wiechen 2021¹⁰	102		1.9%	1.9%	0.2%, 6.9%
Moccetti 2021¹¹	100		1.0%	1.0%	0.2%, 5.4%
Weighted Average	1666	3.9%	4.4%	4.2%	2.0, 8.4%

* CI's were estimated from reported VARC-2 performance using exact binomial methods

Based on these results, the population LBAR Major complication rate is hypothesized to be 4.2%, the weighted average of the above rates. Examining the confidence intervals above, the upper confidence limits for comparably-sized studies range from 5.4% to 19.9%, corresponding to point estimates of 1.0% to 10.7%. A performance goal of 14.2%, which is based on clinical judgement regarding device performance, falls well within this range, indicating that it is constructed in a fashion consistent with prior findings in the literature.

Additionally, though Sponsor does not intend to demonstrate better safety outcomes than with use of the current approved procedure, determining deployment depth of MANTA using the depth locator, the value of 14.2% is more stringent than the performance goal of 19.9% which was accepted for the MANTA VCD PMA study.

Using these inputs, a one-sided alpha of 0.025 and at least 80% power, 69 subjects will provide adequate power to reject the primary safety hypothesis. To ensure an adequate sample size of subjects meeting the 30-day primary safety endpoint, and to account for patient attrition, data from the first 75 consecutive subjects (with a maximum of 15 subjects at any one site to cap enrollment at 20% of subjects enrolled per site) in the Primary Analysis Cohort (PAC) will be analyzed and submitted as to support a PMA supplement for revised labeling to include the U/S-guided method.

Additional subjects will be enrolled as part of the PAC to provide supplementary data in support of future publications for a total of 150 enrolled subjects (with a maximum of 30 subjects at any one site to cap enrollment at 20% of subjects enrolled per site) in the overall study.

Additionally, roll-in subjects (up to 2 per operator per site) using the MANTA VCD will be enrolled to allow investigators to learn how to use the U/S guided therapy with the MANTA VCD. This group will be analyzed separately and not count towards the PAC.

The rate of LBAR Major Complications within 30 days of the procedure will be presented along with the exact one-sided upper 97.5% confidence bound. If this upper confidence bound is less than 14.2%, the study will have met its primary objective.

6 Statistical Analyses and Study Objectives

6.1 Cohort Definitions

Primary Analysis Cohort (PAC): Subjects in the PAC that have had an attempt to use the MANTA VCD with use of U/S to guide placement. The first 75 consecutively enrolled subjects of this cohort will be submitted as a PMA supplement. A total of 150 subjects will make up the total PAC.

Roll-in Cohort: Additionally, up to 2 roll-in subjects per operator using the MANTA VCD will be enrolled to allow investigators to learn how to use the U/S guided therapy with the MANTA VCD. Roll-in subjects will not count towards the 150 subjects making up the PAC.

6.2 Timing of Reports

In addition to the required IDE annual progress reports, there will be two reports prepared: the primary analysis report once 75 subjects have completed their 30 day follow-up (see details below), and a Final Report.

The primary analysis report will be prepared once the first 75 consecutively enrolled subjects in the PAC have either completed their 30 day visit or withdrawn from the trial. The primary safety endpoint will include subjects from the 75 subjects only unless more than 15 subjects have been enrolled at a single site. If this unlikely situation occurs, then the first 15 enrolled subjects from that site will be included to achieve no more than 20% of patients coming from a single site. All remaining endpoints will summarize what data are available at that time as endpoints are intended to be descriptive in nature and involve no hypothesis testing.

A final report will be prepared once the trial is complete, where all subjects have completed their 12 month visit or withdrawn from the study and sites are closed. All available subject data will be included at this time. A 95% confidence interval for the main safety endpoint will still be prepared but the basis for approval is intended to use the primary analysis report.

6.3 Primary Safety Endpoint: LBAR Major complications

Endpoint: Large Bore Access-site Related VARC-2 Major Vascular (LBAR Major) Complication within 30 days (adapted from VARC-2 Definitions)¹⁰

- Access site or access-related vascular injury (dissection, stenosis, perforation, rupture, arterio-venous fistula, pseudoaneurysm, hematoma, irreversible nerve injury, compartment syndrome, percutaneous closure device failure) leading to death, life threatening or major bleeding, visceral ischemia, or neurological impairment OR
- Distal embolization (noncerebral) from a vascular source requiring surgery or resulting in amputation or irreversible end-organ damage OR

- The use of unplanned endovascular or surgical intervention associated with death, major bleeding, visceral ischemia or neurological impairment OR
- Any new ipsilateral lower extremity ischemia documented by patient symptoms, physical exam, and/or decreased or absent blood flow on lower extremity angiogram OR
- Surgery for access site-related nerve injury OR
- Permanent access site-related nerve injury

AEs will be reviewed by the CEC to determine if they meet one or more of these criteria and this adjudication for endpoint classification will be used in analysis.

Hypothesis:

The primary safety hypothesis is that the LBAR Major complication rate (proportion of subjects with one or more) is less than the Performance Goal of 14.2%, as follows:

$$H_0: \pi \geq 0.142$$

vs.

$$H_A: \pi < 0.142,$$

where π is the population LBAR Major Complication rate within 30 days.

The primary safety hypothesis is that the rate of LBAR Major complications within 30 days of the procedure is less than the performance goal of 14.2%.

Stated in words, the hypothesis is:

Null hypothesis: The rate of LBAR Major complications within 30 days of the procedure not less than the performance goal of 14.2%

Alternate hypothesis: The rate of LBAR Major complications within 30 days of the procedure is less than the performance goal of 14.2%

Subjects to include:

The first 75 chronologically enrolled subjects in the Analysis Cohort where an attempt to use the MANTA device is made (enrolled subjects without an attempt will not be included).

Statistical Analysis:

The proportion of subjects with a LBAR Major Complication at 30 days post procedure will be summarized as number, percent and exact 95% 2-sided confidence interval for the calculated proportion. The probability of experiencing at least one LBAR Major complication in 30 days post procedure will be tested versus the performance goal using an exact binomial test comparing to a one-sided alpha of 0.025.

6.4 Secondary Endpoints

6.4.1 Secondary Endpoint 1: Time to Hemostasis (Effectiveness)

Endpoint:

The elapsed time between MANTA deployment (withdrawal of sheath from artery and first observed and confirmed arterial hemostasis (no or minimal subcutaneous oozing and the absence of expanding or developing hematoma). Time to Hemostasis should be inclusive of any time that manual or mechanical pressure is applied specifically to stop arterial bleeding. Do not include time spent when light digital or mechanical pressure is done to treat oozing, or if short manual compression is done as a preventative measure as part of standard of care. Exact times will be collected on electronic Case Report Forms (eCRFs).

Subjects to include: All subjects in Analysis Cohort with a procedure attempt will be included in this analysis.

Statistical analysis: The time to hemostasis will be summarized using descriptive statistics including mean, standard deviation, median, interquartile range, minimum and maximum, and mean time will be calculated.

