6.4.4 Secondary Endpoint 4: Time to Ambulation (Effectiveness)

Endpoint: The elapsed time between MANTA deployment (withdrawal of MANTA sheath from artery) and when ambulation is achieved (subject standing and walking at least 20 feet/6 meters without re-bleeding) as collected on eCRFs.

Subjects to include: All subjects in Analysis Cohort with a procedure attempt will be included in this analysis.

Statistical analysis: The time to ambulation will be summarized using descriptive statistics including mean, standard deviation, median, interquartile range, minimum and maximum, and mean time will be calculated.

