6.4.5 Secondary Endpoint 5: Treatment Success (Effectiveness)

Endpoint: A subject will be considered a Treatment Success if he/she has Time to Hemostasis ≤10 minutes and has no LBAR Major Complications within 30 days.

Subjects to include: All subjects in Analysis Cohort with a procedure attempt will be included in this analysis.

Statistical analysis: The number of subjects and percentage of patients will be calculated for the percentage of subjects with treatment success.

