Every effort will be undertaken to limit premature discontinuations and ascertain completeness of data collection throughout the course of the study. It is unlikely that there would be missing data for the LBAR Major complication endpoint as a 30 day follow-up visit is typically standard of care for TAVR patients; therefore all subjects with an attempted procedure are expected to be followed for at least 30 days. The 12 month follow up assessment will be conducted via phone; sites will ensure that subject contact details are on file correctly when concluding the 30 day visit.

No imputations will be made for missing endpoint data. All available data will be summarized for any summary provided the subject has a procedure attempt.

If an onset date for an AE is incomplete, every effort will be made by the clinical team to identify and collect a valid date from the site, but in case any are incomplete, then the following rules will be used:

- If the day of the month is missing, the first of the month will be used unless it precedes the procedure date. Then the procedure date will be used.
- If the month is missing the date of the procedure will be used.
- No year is expected to be missing as the follow-up is quite short, but the date of procedure will be used if missing the year.

9 Appendices:

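### Time to Ambulation, and possibly Time to Hemostasis, is summarised only in subjects who reach the event, and Treatment Success has no rule for a missing time

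*SAP*

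**What the plan says.** Time to Hemostasis (SAP 6.4.1) runs from deployment, meaning sheath withdrawal, to confirmed arterial hemostasis. On pressure, the definition says "Time to Hemostasis should be inclusive of any time that manual or mechanical pressure is applied specifically to stop arterial bleeding". The analysis set is broad: "All subjects in Analysis Cohort with a procedure attempt will be included in this analysis". The summary is an ordinary descriptive one: "The time to hemostasis will be summarized using descriptive statistics including mean, standard deviation, median, interquartile range, minimum and maximum".

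Time to Ambulation (SAP 6.4.4) starts at the same point and ends "when ambulation is achieved (subject standing and walking at least 20 feet/6 meters without re-bleeding) as collected on eCRFs". It has the same analysis set and the same kind of summary: "The time to ambulation will be summarized using descriptive statistics including mean, standard deviation, median, interquartile range, minimum and maximum". Protocol 8.4 has sites record the ambulation time once the subject walks successfully, including after a failed first try.

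For Treatment Success (SAP 6.4.5), "A subject will be considered a Treatment Success if he/she has Time to Hemostasis ≤10 minutes" and no LBAR Major complication within 30 days.

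SAP section 8 sets the missing-data rule: "No imputations will be made for missing endpoint data". Whatever is available is summarised, provided there was a procedure attempt. Protocol 15.5 says the same. Protocol 7.6 defines an attempt as insertion of the MANTA sheath.

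**The concern.** Both endpoints are times to an event that an attempted subject may not reach. The analysis sets name all attempted subjects, but a subject without a time cannot enter a mean or a median. Under the available-data rule that subject drops out, and the reason for the absence (death, immobility, no deployment, conversion) is related to outcome. The SAP gives no censoring, ranking or non-reacher rule.

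The same gap reaches a percentage. Unplanned stenting or surgery that does not meet the Major criteria counts as LBAR Minor (SAP 6.5). For such a subject, Time to Hemostasis is the only component that can make Treatment Success a No. If that time is absent, the SAP does not say whether the subject is a failure or leaves the denominator.

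These figures will be read. Protocol 8.3.1 calls Time to Hemostasis an important secondary endpoint, the US indication in Protocol 2.2 mentions reduced time to hemostasis, and the first 75 subjects support a labelling supplement.

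**Working it through.** The plan states no expected Time to Hemostasis, Time to Ambulation or number of missing times, so there is no planned figure to reproduce. The check has two parts: who can lack a time, and how much that could matter under stated assumptions.

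**Who can lack a time**

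| Attempted subject | Time to Hemostasis | Time to Ambulation |
|---|---|---|
| Bleeds, treated by compression | Recorded and long; pressure time counts | Recorded if the subject later walks |
| Sheath inserted, no deployment | No defined start | No defined start |
| Converted to stent or surgery | No stated rule; a time may or may not be recorded | Recorded if there was a deployment and the subject later walks |
| Dies or never walks | Depends on whether hemostasis came first | None |

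**Effect on the median.** If *k* of *n* attempted subjects have no time and are ranked longest, the median of the recorded times sits at percentile 50 × (*n* − *k*)/*n* of all attempted subjects. With *n* = 75:

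- *k* = 1: 50 × 74/75 = 49.3
- *k* = 3: 50 × 72/75 = 48.0
- *k* = 8: 50 × 67/75 = 44.7

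**Effect on the mean (illustration for Time to Hemostasis).** Assume the other subjects average *b* = 0.40 to 0.83 min. These are the medians of 24 s and 50 s in Protocol 3.3 and 3.4, used in place of means, which are not given. Assume the absent times would have been *t* = 13 to 37 min, the range of the three hemostasis failures in Protocol 3.2. That range is only a stand-in for length: those three subjects had recorded times, and that study timed its success criterion from suture cutting. Mean over all = ((75 − *k*) × *b* + *k* × *t*)/75:

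- *k* = 1: (74 × 0.40 + 13)/75 = 0.57 to (74 × 0.83 + 37)/75 = 1.32 min
- *k* = 2: 0.74 to 1.80 min
- *k* = 3: 0.90 to 2.28 min

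The mean of the recorded times alone would be 0.40 to 0.83 min.

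**A possible scale for *k*.** In the US pivotal study (Protocol 3.3), covered stent (4), balloon (2) and surgery (2) total 8/263 = 3.0%. That would be 0.030 × 75 = 2.3 of 75, or 0.030 × 150 = 4.6 of 150. The protocol does not say that any of these eight lacked a hemostasis time, so this is a scale for interventions and not an estimate of missing times.

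**Treatment Success (assumed illustration).** Take 150 attempted subjects, 3 failures for other reasons, and *k* non-Major conversions without a time:

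| *k* | *k* leave the denominator | *k* scored No | Difference |
|---|---|---|---|
| 1 | 146/149 = 98.0% | 146/150 = 97.3% | 0.7 points |
| 3 | 144/147 = 98.0% | 144/150 = 96.0% | 2.0 points |
| 5 | 142/145 = 97.9% | 142/150 = 94.7% | 3.3 points |

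The values of *k* and the 3 other failures are assumptions.

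**The case against.** A reader might infer that closure failures in general drop out of Time to Hemostasis, so that more failures give a cleaner-looking distribution. The documents do not support that. The endpoint ends at confirmed hemostasis and does not require the device to have achieved it. Compression time counts, and Protocol 8.3.1 tells sites to check often and declare hemostasis promptly when compression is needed. The three failures in the EU pre-market study had recorded times.

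Other points also limit the concern:

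- The SAP lists median, interquartile range, minimum and maximum as well as mean and SD, so long recorded times remain visible.
- Technical Success and Ambulation Success are reported over all attempted subjects, and LBAR Minor captures device failure, stenting and surgery. A rise in failures would show there.
- Few ambulation times should be missing. Subjects unable to walk 6 m unaided at baseline are excluded (Protocol 7.3, criterion 12), later ambulation is still recorded, and discharge readiness includes walking 6 m (Protocol 8.5).
- SAP 6.2 makes these endpoints descriptive, with no hypothesis test.
- On a plain reading of SAP 6.4.5, a subject with no Time to Hemostasis has not met the 10-minute condition and is a non-success.

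All of this stands, and it narrows the point without removing it. No companion endpoint puts non-reachers back into the time summaries. The plain reading of Treatment Success competes with the available-data rule in SAP section 8, and the SAP does not say which governs.

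**Conclusion.** The concern holds in a limited form. Time to Ambulation is conditional on having walked. Time to Hemostasis may be conditional on deployment and on closure without conversion. Treatment Success has an unsettled denominator for non-Major conversions that lack a time.

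For any subject without a time, the bias is towards faster values, provided the subject would have ranked among the longest. It is small on the median (49.3rd to 44.7th percentile for 1 to 8 missing of 75) and larger on the mean. In the illustration, 2 missing of 75 hide about 0.3 to 1.0 min, from *k* × (*t* − *b*)/75: 2 × (13 − 0.83)/75 to 2 × (37 − 0.40)/75. The Treatment Success difference of 0.7 to 3.3 points rests wholly on assumed counts.

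The actual number affected cannot be derived from the documents. It would therefore go too far to say that the device will look faster than it is; the summaries may look somewhat faster. The primary safety conclusion is untouched.

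**What to change.** In SAP 6.4.1 and 6.4.4:

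- Keep every attempted subject in the denominator. Count those who never reach the event (no deployment, conversion with no recorded time, death first, never walked) as not reaching it, with the longest rank.
- Make the median and quartiles over all attempted subjects the main summary. Any mean, SD and maximum should be labelled as describing recorded times only.
- Print the number without a time, by reason, beside each summary. List separately any subject who reached the event but whose time was not recorded.
- Say whether a time is to be recorded after conversion to a stent or surgery.

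In SAP 6.4.5, state that an attempted subject with no Time to Hemostasis because of alternative closure or surgery, no deployment, or death is Treatment Success = No and stays in the denominator.

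Ranking non-reachers longest assigns no numerical value, so it can sit beside the no-imputation rule. The cost is SAP wording, revised table shells and slightly less favourable descriptive figures. A full time-to-event curve is optional for a descriptive endpoint.
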